10.7 ADVERSE EVENTS MONITORING

All events will be managed and reported in compliance with all applicable regulations, and included in the final CSR.

11 STATISTICAL CONSIDERATIONS

11.1 DETERMINATION OF SAMPLE SIZE

The sample size/power calculations were performed based on the primary endpoint. Assuming a common standard deviation (SD) of 1.2% and using a 2-sided test at a 0.05 α -level, 280 patients in the sotagliflozin 400 mg arm and 140 patients in the placebo arm will provide at least 95% power to detect a treatment difference of 0.5% in mean HbA1c change from Baseline to Week 18 between sotagliflozin 400 mg and placebo.

A sample size of 140 patients in the sotagliflozin 200 mg arm and 140 patients in the placebo arm will provide 80% power to detect a treatment difference of 0.4% in mean HbA1c change from Baseline to Week 18 between sotagliflozin 200 mg and placebo (SD 1.2%; 5% significance level 2-sided).

The total sample size will be 560 patients to be randomized (280 patients in the sotagliflozin 400 mg arm; 140 patients in the sotagliflozin 200 mg arm; 140 patients in the placebo arm).

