8.2.1.3 Dose titration and modification

Lantus will be titrated during the 4-week single-blind Run-in Phase and if necessary after 18 weeks of the core Treatment Period to reach and maintain the target fasting glucose.

The target range for fasting (pre-breakfast/pre-injection if available) blood glucose is 80-100 mg/dL (4.4 to 5.6 mmol/L) avoiding hypoglycemia.

During Run-in (Week -4 to Week -1): after initiating the study provided basal insulin, Lantus, the insulin dose will be up-titrated every 3 days (twice per week) until the patient reaches the target fasting blood glucose according to the recommended regimen (Table 2). The dose adjustments will be made in consultation with the study site either at site visits, phone visits, or unscheduled phone contacts. At the end of Run-in, patients with HbA1c $\geq 7.0\%$ measured at Visit 5 (Week -1) are eligible to be randomized to receive the IMP treatment (sotagliflozin 200 mg, sotagliflozin 400 mg or placebo) on top of Lantus.

During the randomized core Treatment Period (Weeks 0 to 18): no insulin titration should be implemented.

For patients with HbA1c $< 7.5\%$ measured at Week-1, a 10% reduction in the Lantus dose at the randomization may be considered by the Investigator as needed, to reduce a potential risk of hypoglycemia.

Lantus daily dose will remain stable ($< \pm 10\%$ from the dose at randomization, or $< \pm 4$ units, whichever is less) unless it is deemed necessary by the investigator to reduce or increase the dose for safety reasons (ie, severe hypoglycemia or AE/SAE) or the patient has met the hyperglycemic threshold for rescue therapy. In such a case, rescue assessment will apply and be implemented (Section 8.2.4). Increase and optimization in Lantus dose will be the first step of rescue therapy prior to initiation of prandial insulin or GLP-1 receptor agonists.

After the core Treatment Period (Weeks 19 to 52): if the target fasting SMBG level is not achieved at the end of Week 18, insulin dose should be continuously up-titrated to maintain the fasting SMBG in the target range until the EOT. Titration will be done on a weekly basis, or as frequently as deemed necessary by the Investigator.

Lantus dose adjustment is based on fasting SMBG values using study glucose meter that displays results already converted to plasma glucose concentration. Regular self-monitoring of plasma glucose is very important in order to achieve the blood glucose targets. It is recommended to

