11.4.2.1 Analysis of primary efficacy endpoint

The statistical test will be two-sided tests at a nominal 5% significance level.

Analysis of the primary efficacy endpoint (change from Baseline to Week 18 in HbA1c) will be performed using the ITT population, using HbA1c measurements obtained from visits during the study, including those obtained after IMP discontinuation or introduction of rescue therapy.

The primary efficacy endpoint of change in HbA1c from Baseline to Week 18 will be analyzed with missing values imputed by control-based multiple imputation method under the missing not at random framework.

- For placebo patients, missing data will be imputed based on the placebo group data
- For patients in the sotagliflozin groups, missing data will be imputed as if the patients were on placebo group throughout the study, where all patients' measurements including the on-treatment measurements will be considered as if the measurements were from the placebo group in the imputation model.

Each of the complete datasets will be analyzed by the analysis of covariance (ANCOVA) model with treatment groups (sotagliflozin 400 mg, sotagliflozin 200 mg, placebo), randomization strata of Week -1 HbA1c ($\leq 8.5\%$, $> 8.5\%$), randomization strata of Week -1 SBP (< 130 mmHg, ≥ 130 mmHg), randomization strata of sulfonylureas use at Week -1 (yes, no), and country as fixed effects, and Baseline HbA1c value as a covariate. Results from each complete dataset will be

combined to provide the adjusted mean change in HbA1c from Baseline to Week 18 for the sotagliflozin 400 mg arm and placebo arm, as well as the between-group difference (comparing sotagliflozin 400 mg arm versus placebo) and the 95% confidence interval (CI) using contrast statements.

Summary statistics (for Screening value, Baseline value, observed values, and observed changes from Baseline) at scheduled visits will be provided for each treatment group. The summary will include the number of observations, mean, SD, standard error (SE), minimum, median, and maximum. Graphical presentations will also be used to examine trends over time using mean values (\pm SE) and mean changes from Baseline (\pm SE) at each of the scheduled visits (using OC).

Assessment of treatment effect by subgroup

Descriptive analyses will be performed on the primary endpoint to summarize the treatment effects across subgroups defined by the following Baseline or Screening factors:

- Race
- Ethnicity (Hispanic, Not Hispanic)

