11.4.2.4 Multiplicity considerations

To control for the family wise type I error, a fixed-sequence testing procedure will be applied to the primary and key secondary endpoints to the following order:

Once the main study primary variable (change from Baseline to Week 18 in HbA1c comparing sotagliflozin 400 mg versus placebo) is statistically significant at $\alpha = 0.05$ (2-sided), a hierarchical testing procedure will be performed to test the following main study secondary efficacy variables by the following prioritized order. The testing will stop as soon as an endpoint is found to be not statistically significant at $\alpha = 0.05$ (2-sided).

- Comparing sotagliflozin 400 mg versus placebo:
 - Change from Baseline to Week 18 in FPG
 - Change from Baseline to Week 18 in BW
 - Change from Baseline to Week 12 in SBP for patients with Baseline SBP ≥ 130 mmHg
 - Change from Baseline to Week 12 in SBP for all patients
 - Change from Baseline to Week 52 in HbA1c
 - Change from Baseline to Week 52 in BW
- Comparing sotagliflozin 200 mg versus placebo:
 - Change from Baseline to Week 18 in HbA1c
 - Change from Baseline to Week 18 in BW
 - Change from Baseline to Week 18 in FPG
 - Change from Baseline to Week 12 in SBP for patients with Baseline SBP ≥ 130 mmHg
 - Change from Baseline to Week 52 in HbA1c
 - Change from Baseline to Week 52 in BW

No multiplicity adjustment will be made on other secondary efficacy variables than mentioned above.

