1.3 DETERMINATION OF SAMPLE SIZE

The sample size/power calculations were performed based on the primary endpoint, change in HbA1c from baseline to Week 18 between sotagliflozin 400 mg and placebo. Assuming a common standard deviation (SD) of 1.2% and using a 2-sided test at a 0.05 α -level, 280 patients in the sotagliflozin 400 mg arm and 140 patients in the placebo arm will provide at least 95% power to detect a treatment difference of 0.5% in mean HbA1c change from Baseline to Week 18 between sotagliflozin 400 mg and placebo.

A sample size of 140 patients in the sotagliflozin 200 mg arm and 140 patients in the placebo arm will provide 80% power to detect a treatment difference of 0.4% in mean HbA1c change from Baseline to Week 18 between sotagliflozin 200 mg and placebo (SD 1.2%; 5% significance level 2-sided).

The total sample size will be 560 patients to be randomized (280 patients in the sotagliflozin 400 mg arm; 140 patients in the sotagliflozin 200 mg arm; 140 patients in the placebo arm).

The sample size/power calculations for the CGM sub-study are based on the primary variable, change from Baseline to Week 19 in the percentage of time within the target range of 70 to 180 mg/dL over 24 hours for sotagliflozin 400 mg as compared to placebo. Assuming a common standard deviation of 18%, a common missing rate of 15% and using a 2-sided test at a 0.05 α -level, 66 patients in the sotagliflozin 400 mg arm and 33 patients in the placebo arm will

Statistical Analysis Plan

Version: Final 2.0

Lexicon Pharmaceuticals Protocol No. EFC14868

Date of Issue: 04 December 2019

[figure not shown]
Covance Study ID:000000155200

provide at least 80% power to detect a difference of 12% of time within the target range of 70 to 180 mg/dL over 24 hours between sotagliflozin 400 mg and placebo

[figure not shown]
The total sample size for the CGM sub-study will be 132 patients (approximately 66 patients in sotagliflozin 400 mg arm, 33 patients in the sotagliflozin 200 mg arm, and 33 patients in the placebo arm).

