2.4.4.1 Analysis of primary efficacy endpoint(s)

The statistical tests will be two-sided tests at a nominal 5% significance level.

Primary analysis

The primary efficacy endpoint of change in HbA1c from baseline to Week 18 will be analyzed by an Analysis of Covariance (ANCOVA) model using HbA1c values measured at baseline and Week 18 (observed or imputed). The missing data at endpoint will be imputed by multiple imputation (MI) methods as detailed below. To be concise, the following texts related to imputation are generalized to accommodate primary as well as continuous secondary efficacy endpoints.

Missing endpoint data at Week 18 (or Week 12 for SBP or Week 52 for HbA1c and BW) visit will be imputed using a model built separately in each treatment group and estimated from the patients in the same treatment group who prematurely discontinue the IMP before the Week 18 (or Week 12 for SBP or Week 52 for HbA1c and BW) visit but have the measurement for the endpoint (retrieved dropouts). The imputation model will include the randomization strata and the corresponding baseline value. In cases of non-convergence during the imputations, the offending stratum will be identified and then will be dropped from the model. Considering that the number of patients in each treatment group who discontinue the IMP but have the measurement for the endpoint is expected to be small, a simple imputation model based on regression will be used with baseline measurement included as the predictor. This will serve as the primary model of imputation for missing data should sampling criteria be satisfied (see below).

An alternative (back-up) imputation method will be used if the number of patients who prematurely discontinue the IMP before the Week 18 (or Week 12 for SBP or Week 52 for HbA1c and BW) visit but have the measurement for the endpoint is <5 in any treatment groups (ie, not sufficient retrieved dropouts to support the imputation method described above). This criterion will be assessed for each primary or continuous secondary efficacy endpoint.

In the back-up imputation method, missing post-baseline endpoint values at Week 18 (or Week 12 for SBP or Week 52 for HbA1c and BW) will be imputed by washout multiple imputation (MI) method under the missing not at random (MNAR) framework.

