Missing endpoint data at Week 18 (or Week 12 for SBP or Week 52 for HbA1c and BW) in the sotagliflozin group(s), as well as in the placebo group are imputed from a model estimated from patients in the placebo group who have the endpoint data available.

For patients in the sotagliflozin 400 mg and 200 mg groups with missing data at Week 18 (or Week 12 for SBP or Week 52 for HbA1c and BW), their missing values will be imputed using observed baseline and the observed primary endpoint data from placebo completers; no intermittent values from either placebo or the active treatment groups will be used.

For placebo patients, missing data will be imputed based on the placebo group data. Intermittent observed values will be used while imputing missing values at Week 18 (or Week 12 for SBP or Week 52 for HbA1c and BW). In cases that a non-monotone missing data pattern occurs at the intermediate visits, these data points will be first imputed in the placebo group using the Markov Chain Monte Carlo (MCMC) option in PROC MI to achieve a monotone missing pattern for all placebo patients. The Week 18 (or Week 12 for SBP or Week 52 for HbA1c and BW) endpoint values will be subsequently imputed from the multiple copies of the original dataset where each copy will have a monotone missing pattern.

The imputation models for the washout MI method will include the randomization strata and the corresponding baseline value. Missing data will be imputed using the regression method. In cases of non-convergence during the imputations, especially for the MCMC application in the placebo non-monotone datasets, graphical measures (eg, trace and autocorrelation plots) will be used to identify the offending variable and once detected, that variable(s) will be dropped from the model and the imputations will be re-run. These re-run models will use the same seed number and number of imputations as used in the original models.

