2.4.4.4 Multiplicity issues

To control for the family wise type I error, a fixed-sequence procedure will be applied to the primary and key secondary endpoints to the following order:

Once the main study primary variable (change from Baseline to Week 18 in HbA1c comparing sotagliflozin 400 mg versus placebo) is statistically significant at $\alpha = 0.05$ (2-sided), the following secondary efficacy variables will be tested in the following prioritized order. The testing will stop as soon as an endpoint is found to be not statistically significant at $\alpha = 0.05$ (2-sided).

- Comparing sotagliflozin 400 mg versus placebo:
 - Change from Baseline to Week 18 in FPG
 - Change from Baseline to Week 18 in BW.
 - Change from Baseline to Week 12 in SBP for patients with Baseline SBP ≥ 130 mmHg
 - Change from Baseline to Week 12 in SBP for all patients

-
- Change from Baseline to Week 52 in HbA1c
 - Change from Baseline to Week 52 in BW
 - Comparing sotagliflozin 200 mg versus placebo:
 - Change from Baseline to Week 18 in HbA1c
 - Change from Baseline to Week 18 in BW
 - Change from Baseline to Week 18 in FPG.
 - Change from Baseline to Week 12 in SBP for patients with Baseline SBP \geq 130 mmHg
 - Change from Baseline to Week 52 in HbA1c
 - Change from Baseline to Week 52 in BW

If any hypothesis is found to be not statistically significant, the testing procedure will be stopped and the following hypotheses will not be tested.

No multiplicity adjustment will be made on other secondary efficacy variables than mentioned above.

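### Does the 80% power stated for 200 mg need restating because that test comes eighth in a stop-on-failure sequence?

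*Protocol*

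**What the plan says.** Protocol 11.1 bases the sample size on the primary endpoint, the 400 mg comparison of HbA1c change at Week 18: 280 against 140 patients, difference 0.5%, SD 1.2%, power at least 95%. It then adds one sentence for the lower dose: 140 against 140 "will provide 80% power to detect a treatment difference of 0.4% in mean HbA1c change from Baseline to Week 18". SAP 1.3 repeats it ("will provide 80% power to detect a treatment difference of 0.4"). The randomized total, 560, equals the powered total.

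The multiplicity sections (Protocol 11.4.2.4, SAP 2.4.4.4) set one fixed order at two-sided 0.05. The 400 mg primary is followed by six 400 mg secondaries: FPG at Week 18, body weight at Week 18, SBP at Week 12 in patients with baseline SBP of at least 130 mmHg, SBP at Week 12 in all patients, HbA1c at Week 52 and body weight at Week 52. HbA1c at Week 18 for 200 mg comes next, in eighth place. The protocol says "The testing will stop as soon as an endpoint is found to be not statistically significant"; the SAP says "the testing procedure will be stopped and the following hypotheses will not be tested".

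On missing data, Protocol 11.4.2.1 says that for sotagliflozin patients "missing data will be imputed as if the patients were on placebo group throughout the study". SAP 2.4.4.1 first uses a model "estimated from the patients in the same treatment group who prematurely discontinue the IMP" but have the endpoint measured. Its back-up, if any arm has fewer than five such patients, has values "imputed from a model estimated from patients in the placebo group who have the endpoint data available".

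**The concern.** A reader may take the 80% as the chance that the trial confirms a 0.4% effect of 200 mg. It is not that, for two reasons.

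- **Sequence.** The 200 mg test is reached only if seven earlier tests all succeed. Neither document gives a power for any of the six secondaries, or for 200 mg within the sequence. One of the six is HbA1c at Week 52, by which time basal insulin has been titrated in every arm: Protocol 8.2.1.3 says that, if the target is not met at Week 18, "insulin dose should be continuously up-titrated to maintain the fasting SMBG in the target range until the EOT". A shared fasting target could narrow the difference between arms.
- **Missing data.** The calculation has no allowance for missing values. Imputing missing sotagliflozin values as if from placebo pulls the estimated effect toward zero.

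If the real chance were far below 80%, the 200 mg arm would be less likely to yield a confirmatory result than the sample-size section suggests, and a 200 mg hypothesis that failed or was never tested would be easy to misread.

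**Working it through.** **Inputs (Protocol 11.1, SAP 1.3).** n = 280, 140, 140; SD 1.2%; differences 0.5% (400 mg) and 0.4% (200 mg); two-sided 5%, critical value 1.96.

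**1. Reproduce the stated figure.**

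SE(200 v placebo) = 1.2 × √(1/140 + 1/140) = 0.1434. 0.4/0.1434 = 2.789. Power = Φ(2.789 − 1.960) = 79.6%; noncentral t on 278 df gives 79.4%. The stated 80% is right to rounding.

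**2. Reproduce the 400 mg figure.**

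SE = 1.2 × √(1/280 + 1/140) = 0.1242. 0.5/0.1242 = 4.025. Power = 98.1% (98.0% by t), consistent with at least 95%.

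**3. Add the gate for which Protocol 11.1 gives inputs.**

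The two contrasts share the placebo arm, so their correlation is (1/140) / √[(1/280 + 1/140)(2/140)] = 0.577. The bivariate normal probability that both exceed 1.96 is 79.2%. The loss is 79.6 − 79.2 = 0.4 point.

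**4. Is 79.2% a firm ceiling?**

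Only if 1.2% is the residual SD. The analysis is an ANCOVA with baseline HbA1c, strata and country, and the documents do not say whether 1.2% is raw or adjusted. Repeating steps 1 and 3:

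| Residual SD | 200 mg alone (z) | Jointly with 400 mg primary |
|---|---|---|
| 1.20 | 79.6% | 79.2% |
| 1.19 | 80.3% | 79.9% |
| 1.18 | 81.0% | 80.5% |
| 1.10 | 86.0% | 85.8% |

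**5. The six secondary gates (all inputs assumed).**

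If each has the same power q and all are independent of one another and of the Week 18 HbA1c tests, the chance of a 200 mg claim is 0.792 × q⁶: 74.5% at q = 0.99, 58.2% at 0.95, 42.1% at 0.90. With a correlation of 0.6 among the seven 400 mg tests, simulation gives about 77%, 69% and 61%. If HbA1c at Week 52 is the only uncertain secondary (SD 1.2%, correlation with Week 18 of 0.3 to 0.7), the claim has 78% probability at a Week 52 difference of 0.50%, 72–74% at 0.40% and 55–58% at 0.30%.

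**6. Missing data (rates assumed).**

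If 0.4% is an on-treatment effect and missing values behave as placebo, the effect becomes 0.4 × (1 − m). For the 200 mg test alone at SD 1.2% this gives 75.5%, 70.9% and 65.9% at m = 5%, 10% and 15%. If missing data only reduce n, the figures are 77.6%, 75.4% and 72.9%. If 0.4% is already the difference irrespective of stopping treatment, the shrinkage in the first set does not apply. For the SAP's first-line method the effect on power cannot be computed from the documents.

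**The case for a change.** The strongest case for a change is that the documents themselves give reasons to doubt the gates and the margin.

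- The all-patient SBP test includes patients below 130 mmHg, in whom Protocol 4.5 reports no significant Phase 2 effect.
- SAP Table 1 dates the amendment that made the two Week 52 tests secondary endpoints to March 2018. The first patient was enrolled in November 2017, and the current sample-size text does not mention these tests.
- SAP 1.3 allows 15% missing for the CGM sub-study but nothing for the main study.
- The Phase 2 change on 200 mg net of placebo in Protocol 4.3 is 0.52 − 0.14 = 0.38%. That is 0.95 × 0.4%, so the power is the same 75.5% as under 5% dilution.

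The facts stand, and so does the distinction between power for one comparison and the chance of a sequential claim. The large losses do not stand as findings about this plan. The lowest values require seven contrasts of the same two arms to be uncorrelated, although they include HbA1c twice, body weight twice, and SBP in everyone and in a nested subset. The gate with a documented effect points the other way: Protocol 4.5 cites an SBP reduction of 10 to 15 mmHg in patients at or above 130 mmHg. Taking 10 mmHg as the difference from placebo and assuming half the patients qualify (140 against 70) with an SD of 12 to 18 mmHg, power is about 97% to over 99.9%. The Phase 2 trial ran 12 weeks, and its arithmetic is context rather than a planning input here. Protocol 10.3.4 also keeps patients in follow-up after they stop treatment, which limits missing data.

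**Conclusion.** No change is needed. The 80% is a correctly calculated, fully specified power for one comparison taken alone, on complete data. Neither document presents it as the probability of a confirmatory 200 mg result. The only sequential loss computable from the sample-size section's inputs is 0.4 point (79.6% to 79.2%), smaller than the effect of changing the SD from 1.20 to 1.19. The wider ranges, 42–77% through the secondary gates and 66–78% for missing data, depend on assumed gate powers, correlations and missing rates. The lower missing-data figures also require reading 0.4% as an on-treatment effect.

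The inference is sound whatever the in-sequence power is. The fixed order controls the family-wise error rate, and the trial was sized on the 400 mg primary, whose statement holds; by noncentral t it keeps at least 95% power up to about 10% missing even under placebo-based dilution. A 200 mg comparison that fails or is never formally tested is still reported with an estimate and 95% CI under SAP 2.4.4.1 and 2.4.4.2, and those, not planning power, show what the data support. Labelling the 80% as stand-alone with no missing-data allowance would be harmless, but it corrects no wrong number and affects no analysis. This is missing planning detail, not a defect.

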4.3 RATIONALE FOR SELECTION OF DOSE

Both the 200 mg and 400 mg doses are being developed in the Phase 3 program for sotagliflozin for the treatment of T2D. These doses are being tested in several Phase 3 trials, including the current trial in patients with T2D and inadequate glycemic control.

The proposed sotagliflozin 200 mg and 400 mg once daily doses are based on the results of the Phase 2b study LX4211.1-202-DM. In this study sotagliflozin doses of 75 mg once daily, 200 mg once daily, 200 mg twice daily, and 400 mg once daily were tested over a 12-week, double-blind period. The sotagliflozin 200 mg and 400 mg once daily doses were chosen for further evaluation based on their HbA1c lowering effects and the overall safety and tolerability observed at these doses. At 12 weeks, the 200 mg and 400 mg once daily doses lowered HbA1c by a mean of 0.52% and 0.93%, respectively ($p < 0.001$ for both arms), while placebo lowered HbA1c by a mean of 0.14%. Sotagliflozin also produced statistically significant reductions in body weight (BW) (200 mg and 400 mg doses) and systolic blood pressure (SBP) (400 mg dose).

The overall incidences of AEs on sotagliflozin 200 mg and 400 mg once daily doses were similar to placebo.

From a safety perspective, sotagliflozin was well-tolerated across studies. In healthy subjects, sotagliflozin was well-tolerated following single doses up to 2000 mg, and in multiple doses up to 800 mg over 10 days. Furthermore, in a thorough QT study, single doses of sotagliflozin (800 mg and 2000 mg) were well-tolerated and did not prolong the QT interval. Additionally, evaluation of metabolites in urine and plasma of healthy subjects resulted in no safety concerns following single doses of 400 mg sotagliflozin. In patients with T2D, single doses of 400 mg in combination with sitagliptin, and multiple doses up to 400 mg in combination with metformin over 12 weeks were also well-tolerated.

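### Is the 200 mg comparison powered on a difference that the protocol's own Phase 2b data do not support?

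*Protocol*

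**What the plan says.** Protocol 11.1, repeated in the synopsis and in SAP 1.3, gives two power statements. For 400 mg, 280 against 140 on placebo provides "at least 95% power to detect a treatment difference of 0.5% in mean HbA1c change". For 200 mg, 140 against 140 "will provide 80% power to detect a treatment difference of 0.4% in mean HbA1c change from Baseline to Week 18", with the inputs given as "SD 1.2%; 5% significance level 2-sided". No source is named for either difference.

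The only HbA1c results by dose are in Protocol 4.3, from a 12-week Phase 2b study: "the 200 mg and 400 mg once daily doses lowered HbA1c by a mean of 0.52% and 0.93" percent respectively, "while placebo lowered HbA1c by a mean of 0.14" percent.

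In the fixed sequence (Protocol 11.4.2.4, SAP 2.4.4.4), Week 18 HbA1c for 200 mg comes after the primary test and six secondary 400 mg tests, so it is eighth. It is also the first of six 200 mg tests. The rule is "The testing will stop as soon as an endpoint is found to be not statistically significant"; the SAP adds "If any hypothesis is found to be not statistically significant, the testing procedure will be stopped and the following hypotheses will not be tested".

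**The concern.** Set beside Protocol 4.3, the two planning differences do not move together. The 400 mg figure lies well below what Phase 2b showed, while the 200 mg figure lies slightly above. The plan thus implies that 200 mg keeps 80% of the 400 mg effect, where Phase 2b suggests about 48%. Any reason for caution about 400 mg, such as the longer follow-up or the titrated insulin background, would seem to apply to 200 mg too.

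If 0.4% is optimistic, the 200 mg arm is too small. The Week 18 HbA1c test gates the other five 200 mg tests, so its marginal power is a ceiling on the chance of any confirmatory 200 mg claim. A non-significant result might then be misread as evidence that the lower dose does not work.

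**Working it through.** **Inputs.** Two-sided alpha 0.05, SD 1.2, differences 0.4 and 0.5, arms of 140, 280 and 140 (Protocol 11.1); reductions of 0.52, 0.93 and 0.14 (Protocol 4.3).

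**Formula.** Normal approximation: power = Φ(d/SE − 1.96), with SE = SD × √(1/n1 + 1/n2). Non-central t results are given beside it.

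**The plan's own figures.**
- 200 mg: SE = 1.2 × √(2/140) = 0.1434. 0.4/0.1434 = 2.789, less 1.96 is 0.829, and Φ = 79.6% (t: 79.4%). The stated 80% is reproduced. The exact requirement for 80% is 142 per arm (t: 143), against 140 planned.
- 400 mg: SE = 1.2 × √(1/280 + 1/140) = 0.1242. 0.5/0.1242 = 4.025, less 1.96 is 2.065, and Φ = 98.1% (t: 98.0%). The claim of at least 95% holds with room to spare; 113 on placebo and 226 on 400 mg would give 95%.

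**Phase 2b differences.**
- 200 mg: 0.52 − 0.14 = 0.38. The plan's 0.4 is 0.02 higher, and 0.4/0.38 = 1.05.
- 400 mg: 0.93 − 0.14 = 0.79. The plan's 0.5 is 0.29 lower, and 0.5/0.79 = 0.63.
- Ratio of 200 mg to 400 mg: 0.38/0.79 = 0.48 in Phase 2b, against 0.4/0.5 = 0.80 in the plan.

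**Cost of the 0.02.** At 0.38: 0.38/0.1434 = 2.649, less 1.96 is 0.689, and Φ = 75.5% (t: 75.2%). This is about 4 points below the power at 0.4. Restoring 80% would take 157 per arm (t: 158).

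**Effect of the covariate.** The analysis is an ANCOVA with the randomization strata and country as fixed effects "and Baseline HbA1c value as a covariate" (Protocol 11.4.2.1). Protocol 11.1 does not say whether 1.2 is the SD before or after adjustment. With an adjusted SD of 1.1, power at 0.38 is 82.1%; with 1.0 it is 88.7%. The break-even SD is 1.13. If 1.2 is unadjusted, that needs a correlation of only about 0.33 between the covariates and the change: 1.2 × √(1 − 0.33²) = 1.13.

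**The case for a change.** The strongest case is the asymmetry, not the 0.02. Suppose 200 mg is scaled in the same proportion as 400 mg: 0.38 × 0.5/0.79 = 0.24. Power is then 38.9% (t: 38.6%) at SD 1.2, and still only 51.8% at SD 1.0. On that reading the 80% is far too generous.

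This needs two steps that the documents do not supply. Nothing says that 0.5% was obtained by reducing 0.79%; both figures can equally be read as target differences worth detecting, stated to one decimal. Nor does anything support carrying the same proportion over to 200 mg. The ratio of 0.48 comes from point estimates quoted without standard errors, in a study that ran 12 weeks and is not described as being on basal insulin. Whether that ratio carries over to Week 18 on titrated Lantus is unknown in either direction, so 0.24% is a hypothetical value and not the protocol's evidence.

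A second argument is that Protocol 11.1 makes no allowance for missing data, whereas SAP 1.3 assumes 15% missing in the CGM sub-study. If 5% to 15% of 200 mg patients contributed no effect, a difference of 0.4 would shrink to between 0.38 and 0.34, and power to between about 75% and 66%. That is fair as an illustration. But the 0.4% is not labelled as being before or after such dilution, and this is a separate question from whether it agrees with Phase 2b.

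What stands is that the basis for 0.4% is not written down, that the 80% is a marginal figure, and that it sits at the planned difference with no reserve. The last is true of any arm sized for 80%.

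**Conclusion.** No change is called for. The power statement is conditional on 0.4%, and on that condition it is right (79.4% to 79.6%). The planned difference agrees with the Phase 2b value at the precision used. The remaining gap is about 4 points of power at SD 1.2 with complete data, and none if the adjusted SD is 1.13 or less.

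The available remedies gain little. Resizing to 158 per arm would add 36 patients (596 in total, keeping 280 on 400 mg), or 72 (632) if 2:1:1 is kept, although no stated power is missed. It is also unrealistic: SAP 1.5 puts first enrolment in November 2017, and SAP version 2.0 is dated December 2019. A stated rationale or a table of power at other differences would be tidier but would alter no estimate, test or decision. The guard against reading a null result as no effect is already planned: Protocol 11.4.2.2 and SAP 2.4.4.1 provide the 200 mg difference from placebo with its 95% CI. The primary comparison, the order of testing and the alpha are untouched.

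This conclusion rests on the documents' SD of 1.2% and on treating 0.38% as a reference point rather than a forecast for Week 18.
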